2.2.3. Treatment Period

Subjects will undergo study treatment duration of 4 weeks of 14N sodium nitrite 20-40 mg three times daily. This is considered appropriate to study benefits of oral nitrite therapy to improve physical function in patients with HFrEF and HFpEF and age-matched controls.

2.2.4. Safety Monitoring:

Subjects will be contacted by phone weekly and this will include symptom review, assessing adverse events, interval histories and medication compliance.

In addition to these phone evaluations, subjects will be encouraged to immediately contact the study investigator and/or the study coordinator with questions, concerns, or to report new symptoms that occur during their study participation. If there are particular concerns that need to be addressed the subject will be asked to return to the EMRC or SMART Center as soon as possible for evaluation. Evaluations will be planned on an individual basis (depending on each individual's circumstances) and may include weight, vital signs, methemoglobin %, medication compliance review, and assessment by the study physician. If appropriate, based upon the evaluation, medical treatments will be provided to subjects, including appropriate referral to physicians or other services at the UPMC.

2.2.5. Medication Compliance

Subjects will self-administer their first dose of study medication under the supervision of the CTRC nurse (physician investigator will be immediately available) in the outpatient CTRC during Visit 3, following completion of all baseline clinic assessments. Subjects will also be dispensed their study medication (42-day supply) for home use, including four 7-day prefilled and labelled pill boxes and drug/symptom diary cards to help with compliance and to help reduce burden or confusion. (Visit 4 may be scheduled up to and on the 42nd day from visit 3 (25-35±5 days); additional drug will be distributed with the initial dispensation if needed to meet the need.) Subjects will return the previously dispensed study medication when they return for Visit 4 approximately 4 weeks later (+1 week if need be for flexibility of scheduling) and medication compliance will be assessed. The study coordinator will review the daily diary card with each phone call evaluation and also assess medication compliance with queries regarding empty pill compartments in the current 7-day box and remaining boxes. In the event that the compliance rate is <80% (subjects' report of doses taken/total doses prescribed at that date & time *100), subjects will be re-educated on medication compliance. If medication compliance repeatedly falls outside of the acceptable range, the study investigators will discuss subject eligibility for continued participation in the study.

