Chronic dietary supplementation of inorganic sodium nitrate in obese, hypertensive, insulin resistant mice lacking the gene for endothelial NO synthase (eNOS) (20) was studied. With a 10 week treatment of a modest dose of sodium nitrate of 0.1 mmol/kg/day (8.5 mg/kg/day) in the drinking water, significant reductions in blood pressure, fasting blood glucose, HbA1C, and proinsulin to insulin ratio were demonstrated, indicating reduced demands on the β -cell for insulin secretion.

Sodium nitrate drug is considered a source of nitrite through salivary nitrate reduction. Despite the plasma nitrite rise following a single oral sodium nitrate dose, Drs. [name], [name] and [name] recently demonstrated in a phase I PK/PD study in 10 normal volunteers that no persistent blood pressure reduction with sodium nitrate 1,000 mg. In contrast, in the same phase I PK/PD study in

10 normal volunteers, they showed blood pressure decline in systolic, diastolic and mean arterial pressures over 3 hours with sodium nitrite 20 mg. The oral sodium nitrite half-life was about 40-minutes and the effects of nitrite only lasted ≤ 6 hours. This was demonstrated by the plasma nitrite levels returning to baseline levels between 3 and 6 hours after nitrite dosing (i.e. the drug was given and gone out of the circulation within 6 hours). Specifically, mean baseline (pre-nitrite dosing) blood nitrite concentrations were 0.129 micromolar with a peak at 30 minutes of 5.5 micromolar, and return to baseline levels between the 3- (0.176 micromolar) and 6-hour (0.103 micromolar) monitoring time points. In addition, there were no serious adverse events when these normotensive individuals received sodium nitrite.

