Subjects will rest for approximately 30 minutes post biopsy while wound is dressed and prior to baseline vitals prior to dosing. Study staff will record a baseline level of symptoms, including shortness of breath, dizziness, lightheadedness for use during weekly phone calls, prior to dosing.

Following biopsy, subjects will receive their first dose of study drug as follows:

- 14N sodium nitrite, 20 or 40 mg per physician order
- Blood pressure (sitting and then standing after 3 minutes), HR, RR, pulse oximeter and methemoglobin will be measured to ensure they are at a steady state before taking the study drug (baseline) and then approximately every 15 minutes for the 2 hours post-drug administration. Any perturbations of concern will be addressed per the Dose Reduction protocol described in Section 2.2.6.
- AE assessment
- Provide a 42-day supply of study drug, pre-filled in 4 weekly pill boxes and an extra bottle and drug diary cards to assist with compliance and reduce burden or confusion. Study staff will review medication administration and use of the drug diary card with all subjects. Study staff or CTCR RN will review biopsy site care with subjects and if indicated, remind subjects to resume their normal anti-coagulation and anti-platelet medications the following day (as indicated).
- 24-hour dietary recall. The study coordinator will collect a second 24-recall of all foods eaten from subjects for analysis for calories, macronutrients, sodium, nitrates and nitrites.

Subjects will be reminded before departure to report promptly any changes in their medication, health or symptoms of concern, not to wait for the weekly call.

Visit 4 (First Completion Assessment visit to be scheduled 25-35±7 days following first dosing of 20-40 mg oral nitrite) Subjects who need more than 42 days' supply of drug due to scheduling later in window will be issued additional at visit 3.

This visit will take place in the EMRC and/or Pepper SMART Center and is identical to visit 2 (approximately 3 hours):

Interval history and brief physical exam: temperature, blood pressure, pulse oximetry for methemoglobin %, breathing rate, heart rate and body weight; additionally, AE and symptom assessment will be collected and medication compliance via drug diary cards and pill boxes will be assessed.

Physical Function Battery:

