- The Kansas City Cardiomyopathy Questionnaire will be used to measure disease-specific health-related quality of life (QOL). This 24-item instrument produces the following scores: Physical Limitation, Symptoms, Symptom Stability, Social Limitation, Self-efficacy, Quality of Life, and two summary measures, and is widely used as a standard by which quality of life, self-efficacy, and other personal perspectives related to functional capacity at baseline and over time. Subjects in the healthy elderly control group will be asked to complete the SF-12.
- 24-hour Dietary recall. The study coordinator will collect a post 24-hour recall of all foods eaten from subjects for analysis for calories, macronutrients, sodium, nitrates and nitrites.

Visit 5 (Final Completion Visit - 2-7 \pm 7 days following Visit 4)

Subjects will be fasting and take their last dose of study drug at home on their usual schedule prior to scheduled testing time. Upon arrival to the CTRC, subjects will be served a standardized breakfast as described in visit 3, then interval history and brief physical exam; temperature, blood pressure, pulse oximetry for methemoglobin %, breathing rate, heart rate and body weight will be documented; additionally, AE and symptom assessment, medication compliance via drug diary cards and pill boxes, and confirmation of last dose will be performed prior to assessment procedures. Prior to the biopsy, study staff will call indicated subjects to hold their anti-platelet and anti-coagulation medications for 1-5 days (depending on the different medications and relative half-lives). This visit will last approximately 2 hours.

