- Blood draw to include: research blood for inflammatory peptides (IL-1, IL-6, IL-15, TNF α), platelet sample and nitrite levels: Two blood samples will be drawn into a 1) heparinized syringe and 2) a cell preparation tube (CPT). Heparinized blood will be immediately centrifuged at bedside to separate plasma and the plasma and red cells separately flash frozen for later nitrite measurements (via reductive chemiluminescence to determine that nitrite levels were increased in the muscle as described). The second tube of blood (CPT tube) will be immediately subjected to differential centrifugation in order to isolate platelets. Platelets will then be subjected to Seahorse extracellular flux analysis in order to measure bioenergetic profile including basal, non-ATP producing, maximal and non-mitochondrial respiratory rates along with glycolytic rate. Extra aliquots will be stored for use in future studies. Total volume of blood drawn will be 56 ml (4 tablespoons)

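### Section 2.2.5 takes the study drug back at Visit 4, although the Visit 5 procedures need a last home dose 2-7 ± 7 days later and no re-issue is described

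*Combined protocol and SAP*

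**What the plan says.** **Return of drug.** Section 2.2.5 (Medication Compliance): "Subjects will return the previously dispensed study medication when they return for Visit 4 approximately 4 weeks later". Compliance is to be assessed on that occasion.

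**Last dose.** Section 2.3.1 places Visit 5 at 2-7 ± 7 days after Visit 4. Subjects "take their last dose of study drug at home on their usual schedule prior to scheduled testing time". Staff then review "medication compliance via drug diary cards and pill boxes, and confirmation of last dose will be performed prior to assessment procedures".

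**Supply.** At Visit 3 subjects receive 42 days of drug, "pre-filled in 4 weekly pill boxes and an extra bottle". Under the Visit 4 heading, those who need more than a 42-day "supply of drug due to scheduling later in window will be issued additional at visit 3". Section 2.2.5 has a similar provision, also attached to Visit 4 scheduling. The Visit 4 procedures check diaries and pill boxes but neither collect nor re-issue drug.

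**What is measured when.** Visit 4 has the exercise, walking, physical performance and grip tests and the quality-of-life questionnaire. Visit 5 has the muscle biopsy and the blood draw, which covers inflammatory peptides, "platelet sample and nitrite levels: Two blood samples will be drawn". Section 2.5 models each outcome at two time points, baseline and 4 weeks.

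**The concern.** A subject who has handed in the drug at Visit 4 has nothing to take at home before Visit 5. If site staff apply 2.2.5 as written, the mechanistic half of the post-treatment data is collected off drug and the functional half on drug, yet section 2.5 treats both as one 4-week time point. The same section correlates changes in skeletal physiology with changes in strength, gait speed and balance. It would then pair off-drug muscle values from Visit 5 with on-drug function values from Visit 4. The plasma nitrite value on which Aim 3 would draw at follow-up would also be off drug.

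The last-dose confirmation at Visit 5 would expose the problem, but only on the day of the biopsy, when the missed doses can no longer be made up.

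**Working it through.** The plan gives no figure to reproduce. The check is on consistency and visit days.

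**1. Which instruction is out of line?**

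- For dosing to Visit 5: the last home dose and its confirmation (Visit 5 procedures); the diary and pill-box review at Visit 5 (same place, and the compliance row of Table 1, marked for both Visits 4 and 5); the post-drug telephone call timed from Visit 5, not Visit 4.
- Weaker support: the provision for more than 42 days of drug. Visit 4 falls on day 35 + 7 = 42 at the latest (section 2.3.1), and section 2.2.5, despite its ±5-day window, also allows it up to day 42. A 42-day supply therefore covers any permitted Visit 4, and more is needed only if dosing goes on afterwards. Because both sentences tie the extra drug to Visit 4 scheduling, this is supporting evidence only.
- For stopping at Visit 4: the return sentence in 2.2.5. The 4-week treatment length in section 2.2.3 does not decide the matter, since Visit 4 itself falls at about 4 weeks.

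**2. Doses lost under a literal 2.2.5** (three doses a day)

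- Nominal gap of 2-7 days: 3 × 2 = 6 to 3 × 7 = 21 doses.
- As a share of all dosing days up to Visit 5: smallest 2/(35 + 2) = 5.4%, largest 7/(25 + 7) = 21.9%.
- With the Visit 5 window the gap can reach 7 + 7 = 14 days, or 42 doses.

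**3. What a gap does to plasma nitrite**

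Section 2.2.2 reports: "The oral sodium nitrite half-life was about 40-minutes", with "plasma nitrite levels returning to baseline levels between 3 and 6 hours after nitrite dosing". At first-order decay:

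- after 6 hours: 360/40 = 9 half-lives, and 0.5^9 = 0.2% of the dose remains;
- after the shortest nominal gap, 48 hours: 48 × 60/40 = 72 half-lives, essentially nothing.

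These kinetics come from a single 20 mg dose in 10 normal volunteers. The documents give no persistence data for muscle or platelet effects, so the loss there cannot be sized.

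**4. Does the supply reach Visit 5 once the return is moved?**

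The supply is 42 × 3 = 126 doses: 4 × 7 × 3 = 84 in the boxes and 126 − 84 = 42 in the bottle.

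| Timing of Visit 5 | Latest day | Shortfall against 42 days |
|---|---|---|
| Nominal (35 + 7) | 42 | none |
| Visit 4 window used (35 + 7 + 7) | 49 | 7 days, 21 doses |
| Both windows used (35 + 7 + 7 + 7) | 56 | 14 days, 42 doses |

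The dispensed supply equals the latest nominal Visit 5 exactly, which again fits dosing to Visit 5. It does not cover late scheduling, and the extra-drug sentences do not mention Visit 5.

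**5. What is counted at the end?** After day 28 doses come from the bottle. The Visit 5 check names diaries and pill boxes. A final return, and a count that includes the bottle, are not stated for that visit.

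**The case against.** The best reply is that the visit-by-visit procedures, which staff actually follow, already agree with one another: Visit 4 checks compliance without collecting drug, Visit 5 expects a home dose, and Table 1 has a compliance review at both. The return sentence sits in a section on compliance and can be read as bringing the drug in to be checked. Much of this stands. It is why the number of subjects affected may be zero, and the enrolment experience reported in section 2.2.2 (10 controls and three heart failure subjects) mentions no missed doses before Visit 5. What it does not do is remove the conflict. Section 2.2.5 says the drug is returned, section 2.2.6 uses returned amounts as an accountability term, and nothing says that the drug goes home again.

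Three stronger readings are tempting, and the documents do not support them.

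- *That Aim 2 would be lost.* Nitrite is also sampled at Visit 3, at baseline and at about 30 minutes and 2 hours after a supervised dose. That evidence does not depend on Visit 5.
- *That off-drug plasma nitrite would distort the mixed models.* Section 2.5 lists skeletal muscle, platelet, gene expression, inflammatory, oxygen uptake and physical function measures as dependent variables. Plasma nitrite is not named.
- *That the half-life figure measures the damage.* No dose-to-draw interval is set for Visit 5, and breakfast, history, examination and compliance review come before the blood draw. Depending on that interval, a fully dosed subject could also be near baseline.

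It is also fair to say that the missing bottle count is partly bookkeeping, since section 2.2.6 already requires dispensed and returned amounts to be recorded.

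**Conclusion.** The conflict is real and should be removed. The return at Visit 4 is the line that is out of step; the intended design, dosing to a last home dose before Visit 5, is clear from the rest of section 2.3.1.

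If 2.2.5 is applied literally, the Visit 5 muscle, gene expression, platelet and inflammatory measures, and the Visit 5 plasma nitrite value relevant to Aim 3, are taken nominally 2-7 days (6-21 doses) off drug. Aim 2 is only partly exposed.

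This rests on three-times-daily dosing and the nominal visit gap, and on no re-issue taking place because none is written. The documents do not show that any subject was off drug at Visit 5, and a reader should not infer that any was. In a study of 30 subjects in three groups, even a few such cases would matter, and preventing them costs very little.

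**What to change.** In section 2.2.5, replace the Visit 4 return with wording to this effect:

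- Subjects bring all pill boxes and the bottle to Visit 4 for a compliance check and take them home again.
- Dosing continues three times daily until the last home dose before Visit 5.
- All remaining drug, including the bottle, is returned and counted at Visit 5.
- The supply issued at Visit 3, topped up at Visit 4 if necessary, must cover the scheduled Visit 5, which can fall as late as day 56 when both windows are used.

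The diary, pill-box and last-dose checks at Visit 5 stay as they are.

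Cost: a few sentences, one extra capsule count in the existing accountability record, and subjects carrying the boxes and bottle to two visits. Late-scheduled subjects need up to 14 more days of drug: 42 doses, so 42 capsules at 20 mg or 84 at 40 mg. No new visit, assay or form is needed.

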2.2.6. Medication Accountability

The study investigators or the study coordinator will document the amount of study drug dispensed and/or administered to subjects, the amount returned by subjects, and the amount received from and returned to the UPMC-IDS. The study drug accountability records will be maintained throughout the course of the clinical trial.

Dose reduction

There is a rare possibility that subjects will have a high methemoglobin level or low blood pressure from the study drug dose during visit 3 or while they are on the drug. If this happens, they may experience lightheadedness or dizziness.

In CTRC:

If this occurs in the CTTC, care will be administered, including fluids and monitoring, to ensure that the problem resolves and patient is stable. The physician investigator will factor relevant subject symptoms and hemodynamics and then decide whether it is appropriate for the subject to proceed with study participation prior to discharge from CTTC. This will include what dose is appropriate and drug dispensing. The same process will be applied to subjects who are initially initiated on 20 mg; however, in these subjects there is relatively greater consideration of withdrawal as no lower dosing options are available.

As outpatient:

Blood pressure and related symptoms. If subjects experience lightheadedness or dizziness after visit 3 while they are on the drug, we request that they call the study coordinator who will inventory their symptoms, compare to baseline levels (measured at pK), and discuss need for interim visit with study physician. If a visit is indicated, we will measure blood pressure, RR, heart rate, and check methemoglobin level by a finger probe. A study physician will evaluate each subject, including:

1. review of all clinical measures,
2. subject history of symptoms,
3. blood pressures pre- and while on drug.

The physician will confirm a management plan including the possibility of lowering dose to 20 mg tid or need to discontinue and drop from the trial. Subjects will be reassessed via phone each day for the next 2 days thereafter to ensure that the patient is stable on the new dose. If stable, subjects will continue with the half dose. However if there are continued symptoms on lower doses, the physician investigator will reevaluate the patient's suitability for continued participation based on symptoms and/or hemodynamics.

If subjects initiated at Visit 3 on the 20 mg dose report symptoms as described above, the same process will be followed; however, the physician may have to withdraw the subject since a dose lower than 20 mg tid is not an option.

Methemoglobin. If subjects report change in skin tone and dizziness or other signs of methemoglobinemia for ≥ 24 hours, an interim visit will be requested. Methemoglobin will be assessed. If greater than 5%, a nitrite dose reduction is proposed from 40 mg three times daily to 20 mg three times daily. Subjects will be contacted via phone for the next 2 days for symptom re-assessment. If symptoms remain resolved, subjects will continue on 20 mg tid. If symptoms persist, subjects will be requested to come in for repeat methemoglobin testing after 3 days. If level persists above 5%, participation in the study for the subject will be discontinued.

Safety of holding anti-platelet or antithrombotic medications

The research physician and the staff under his auspice will guide holding of the antiplatelet and anti-thrombotic medications. In each case, this will be discussed doctor to doctor by the research doctor and the patient's PCP or cardiologist.

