Nine of 10 control subject enrollees into this pilot study have tolerated 40 mg po tid without incident; the one exception was a subject who had a decrease in systolic BP at pK but was asymptomatic. In the three heart failure subjects enrolled to date we have observed a vasoactive response at the pK with the 40 mg dose, such that low blood pressures or symptoms have been observed in the 2 hour monitoring period. This includes subjects with preserved and reduced ejection fraction. Therefore, we postulate the heart failure subjects appear to have a greater vasodilatory response to nitrite and could require a stratified dose based on age and baseline risk for hypotension. To further ameliorate risk, we will serve a standardized meal prior to drug dosing at Visit 3 so that lack of po intake is not a causative factor of hypotension.

In summary, based on the above findings, inclusive of:

- The Joint FAO/WHO ADI for sodium nitrate and nitrite,
- the above DASH diet patterns,
- the recently observed human and rodent effects of nitrate and nitrite on blood pressure and glucose homeostasis, including our PK/PD trial of single doses of oral nitrate and nitrite,
- the open label trial safety and BP findings following a total of 10 subjects' completion,
- the existing inhaled nitrite trial,
- the preliminary findings of the current nitrite protocol with regard to blood pressure in heart failure subjects,

the study investigators believe that a safe and likely therapeutically effective dose of sodium nitrite will be 20-40 mg three times daily (~0.21-0.42 mg/kg body weight per day for a 95 kg subject). The 40 mg sodium nitrite dose selection is equivalent to 12.6 times the ADI.

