Nine of 10 control subject enrollees into this pilot study have tolerated 40 mg po tid without incident; the one exception was a subject who had a decrease in systolic BP at pK but was asymptomatic. In the three heart failure subjects enrolled to date we have observed a vasoactive response at the pK with the 40 mg dose, such that low blood pressures or symptoms have been observed in the 2 hour monitoring period. This includes subjects with preserved and reduced ejection fraction. Therefore, we postulate the heart failure subjects appear to have a greater vasodilatory response to nitrite and could require a stratified dose based on age and baseline risk for hypotension. To further ameliorate risk, we will serve a standardized meal prior to drug dosing at Visit 3 so that lack of po intake is not a causative factor of hypotension.

To summarize, we anticipate the following symptoms by organ system and likely frequency of risk:

Gastrointestinal

- Common: none
- Frequent: none
- Infrequent: dry mouth
- Rare: nausea, abdominal pain and vomiting

Hematologic

- Common: none
- Frequent: none

- Rare: methemoglobinemia

Cardiovascular

- Common: none
- Frequent: hypotension in subjects with heart failure
- Rare: flushing, tachycardia, hypotension in healthy control subjects

Neurologic

- Common: none
- Frequent: none
- Rare: headache, dizziness, seizure, coma

Respiratory

- Common: none
- Frequent: none
- Rare: tachypnea, dyspnea, cyanosis

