Any event meeting #1 or #2 above will be reported immediately to the IRB in their required format. In the event that a participant either withdraws from the study or the PIs decide to discontinue a participant due to a SAE, the participant will be monitored by the co-PIs until (a) a resolution is reached (e.g., the problem has resolved or stabilized with no further change expected), (b) the SAE is determined to be clearly unrelated to the study intervention, or (c) the SAE results in death. Outcomes of SAEs will be regularly reported to the IRB. A summary of the SAEs that occurred during the previous year will be included in the annual progress report as well as in the annual IRB renewal. Suicidal ideation and AEs will be formally assessed immediately after treatment and referrals for further care will be made as needed. In the Informed Consent Form, we will provide specific information about emergency contacts. Participants are instructed to contact [name] during working hours. After hours participants will be provided the information on how to contact the cardiology fellow on call.

Stopping Rule:

For safety reasons, we propose to discontinue participation for any subject who experiences *any of the following*:

1. Methemoglobin greater than 5% after dose lowering
A nitrite dose reduction is proposed from 40 mg three times daily to 20 mg three times daily if this methemoglobin % is reached at any study interim visit, as described in section 2.2.6 (phone report of change in skin tone and dizziness or other symptom suggestive of methemoglobinemia). Follow up symptom assessment for 48 hours and repeat methemoglobin in 3 days will be implemented. If methemoglobin is greater than 5% on the lower nitrite dose, participation in the study for the subject will be discontinued.
2. Blood pressure drop after dose lowering
Blood pressure and related symptoms.

If subjects experience lightheadedness or dizziness after visit 3 while they are on the drug, we request that they call the study coordinator who will inventory their symptoms, compare to baseline (measured at pK) levels, and discuss need for interim visit with study physician. If a visit is indicated, we will measure blood pressure, RR, heart rate, and check methemoglobin level by a finger probe. A study physician will evaluate each subject, including:

- a. review of all clinical measures,
- b. subject history of symptoms,

c. blood pressures pre- and while on drug.

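### A dose lowered to 20 mg in clinic at Visit 3 gets no scheduled study call until day 5 to 9, while a dose lowered later as an outpatient gets calls over the next 2 days

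*Combined protocol and SAP*

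**What the plan says.** The dose reduction text in Section 2.2.6 has an in-clinic branch and an outpatient branch.

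- **In clinic (Visit 3).** The subject is treated and monitored until stable. Before discharge the physician decides whether the subject continues: "This will include what dose is appropriate and drug dispensing". The branch names no contact after discharge.
- **Outpatient, blood pressure symptoms.** This applies to symptoms arising after Visit 3. If the dose is lowered, "Subjects will be reassessed via phone each day for the next 2 days thereafter to ensure that the patient is stable on the new dose".
- **Outpatient, methemoglobin.** After a reduction at an interim visit, "Subjects will be contacted via phone for the next 2 days for symptom re-assessment".

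The Visit 3 text in Section 2.3.1 refers problems during the 2-hour monitoring back to Section 2.2.6 and adds no call. Subjects are reminded at departure to "report promptly any changes in their medication, health or symptoms of concern, not to wait for the weekly call". The stopping rule in Section 5.4.1 headed "Blood pressure drop after dose lowering" repeats only the outpatient process. In Table 1 the first scheduled contact after Visit 3 is phone call 1, at day 7 with a window of ± 2 days.

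**The concern.** The protocol gives its own reason for the outpatient calls: to confirm that the subject is stable on the new dose. That reason applies at least as strongly to a reduction made at Visit 3. Such a subject was judged suitable for 40 mg, reacted to the first dose, and goes home on a dose not yet seen in that person. Yet this subject has the latest scheduled check of the three routes.

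The lower dose is not inert. Section 2.2.2 reports a study in 10 normal volunteers in which "they showed blood pressure decline in systolic, diastolic and mean arterial pressures over 3 hours with sodium nitrite 20 mg". The protocol reports no blood pressure result at 20 mg in heart failure subjects, in whom it postulates a greater vasodilatory response.

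The route may well be used. In the three heart failure subjects enrolled so far, all given 40 mg, "low blood pressures or symptoms have been observed in the 2 hour monitoring period". Section 5.1.1 now lists "Frequent: hypotension in subjects with heart failure". What is at stake is subject safety in the first week at home. No endpoint, sample size or power statement is affected.

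**Working it through.** The plan gives no figure to reproduce. The check sets the three routes side by side and then derives the time to first contact.

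**Routes compared**

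| Route to 20 mg | Trigger | Scheduled contact after the reduction |
|---|---|---|
| In clinic | Reaction during Visit 3 | None named; next is weekly call 1 |
| Outpatient, blood pressure | Symptoms after Visit 3 | Daily phone call for 2 days |
| Outpatient, methemoglobin | Level above 5% at an interim visit | Phone contact for the next 2 days |

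So 2 of 2 outpatient routes have early contact, and 0 of 1 in-clinic routes do. The outpatient calls cannot be read across: one set is limited to symptoms after Visit 3, the other to interim visits.

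**Inputs**
- Call 1: day 7, window ± 2 days (Table 1, reading the time-window row in order: Visit 2, Visit 3, phone call 1).
- Dosing: 3 times daily (Section 2.2).
- First outpatient follow-up call: day 1 after the reduction (Section 2.2.6).
- Visit 3 taken as day 0. Section 2.3.1 schedules Visit 4 by days following first dosing, which supports this.

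**Time and doses before first study-initiated contact**
- Visit 3 reduction: 7 − 2 = day 5 to 7 + 2 = day 9; 5 × 3 = 15 to 9 × 3 = 27 doses.
- Outpatient reduction: day 1; 1 × 3 = about 3 doses.
- Extra delay: 5 − 1 = 4 to 9 − 1 = 8 days.
- Ratio of doses: 15/3 = 5 to 27/3 = 9.

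**Sensitivity to the day convention.** If the first dose counts as day 1, the elapsed time is 4 to 8 days. That gives 4 × 3 = 12 to 8 × 3 = 24 doses, an extra delay of 3 to 7 days, and a ratio of 12/3 = 4 to 24/3 = 8. The contrast stays.

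**Does stability at discharge replace the call?** Section 2.2.2 gives an oral half-life of about 40 minutes, with plasma nitrite back at baseline between 3 and 6 hours. The 2-hour monitoring period is therefore 120/40 = 3 half-lives. Recovery is what one would expect as 40 mg wears off, helped by fluids and the standardized meal. It does not show that 20 mg three times daily at home is tolerated.

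**The case against.** The strongest reply is that the routes are not equivalent. The Visit 3 subject has had sitting and standing blood pressure, heart rate, oximetry and methemoglobin measured about every 15 minutes for 2 hours, with a physician deciding before discharge. The outpatient blood pressure route starts from a phone call, and vital signs are taken only if a visit is judged necessary. On this view the 2-day calls make up for weaker observation. This is true of the 40 mg dose, but the calls are there to check the new dose, and the clinic has not observed that.

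A second reply is that existing cover is substantial: prompt-reporting instructions, symptom diaries, baseline symptoms recorded for comparison, and a physician free to order a call. These limit the harm. But prompt reporting also covers outpatient reductions, and the protocol still added calls there. The diaries are reviewed by the study at the calls and visits, so they do not shorten the gap.

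A third reply is that a reaction to 20 mg would probably come within hours of the first home dose, before any day-1 call, and that a phone call measures no blood pressure. This stands in part. The calls would pick up symptoms after a few doses that a subject had not reported. They would not detect a silent fall in pressure. The dose count is likewise a measure of exposure before contact, not of risk, since plasma nitrite returns to baseline between doses.

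Finally, all reactions to date were at 40 mg, before stratified starting doses and the pre-dose meal, and Section 2.2.6 itself calls such reactions rare. The volunteers given 20 mg had no serious adverse events. This is fair, and is why no number of affected subjects is projected. But heart failure subjects aged 70 to under 80 without recent low pressures can still start at 40 mg.

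**Conclusion.** The concern holds. As written, a subject lowered to 20 mg at Visit 3 has no scheduled study-initiated contact until day 5 to 9, about 15 to 27 doses on, while both outpatient reductions have contact over the next 2 days. That is 4 to 8 days later and 5 to 9 times as many doses, taking Visit 3 as day 0.

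The claim is limited to scheduled contact that the study initiates; subjects can and should call earlier. How many will be affected is unknown. The reactions so far (heart failure 3 of 3, controls 1 of 10, the control without symptoms) arose under the earlier dosing practice. Some who react may be withdrawn before discharge, and those starting on 20 mg cannot be lowered. The safety gain from closing the gap is modest but real, and it should be made because it costs so little.

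**What to change.** In the in-clinic paragraph of Section 2.2.6, add one sentence: any subject whose dose is lowered at Visit 3 is reassessed by phone on each of the next 2 days, as in the outpatient blood pressure route. Optionally, apply the same calls to a subject who started on 20 mg, reacted in clinic and was kept on drug. Add a conditional contact on days 1 and 2 to Table 1.

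The cost is one sentence, one table entry and two short coordinator calls per affected subject. No dose, threshold, visit, procedure or stopping rule changes, and no extra staff are needed.
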